discontinuation. At Baseline, subjects will undergo safety and tremor assessments prior to dosing, will receive their first dose of study drug and will be monitored for safety for one hour following dosing. For one week, subjects will receive 4 mg (or matching placebo) twice daily. Subjects will return to the clinic on Day 8 for safety monitoring and dose up-titration to 8 mg (or matching placebo) twice daily. At Day 15 (Week 3) subjects will return to clinic for safety and efficacy assessments and final dose up-titration to 10 mg (or matching placebo) twice daily. The final efficacy visit will occur at Day 28 (Week 4). A final safety visit will occur at Day 35 (Week 5). Should subjects experience intolerable adverse events (AEs) at 4 mg BID, 8 mg BID or 10 mg BID, the dose may be decreased at Day 8 or Day 15 to the next lowest dose one time (or 2 mg BID in the case of the 4 mg BID dose). A dose reduction may be made if necessary prior to scheduled visits at Day 8 or Day 15. Re-up-titration is not allowed. Subjects not tolerating the next lowest dose or not tolerating 2 mg BID will be withdrawn from treatment. The study safety representative should be notified as soon as is feasible when a dose reduction is made.

Study Population:***Inclusion Criteria***

1. Signed informed consent form (ICF) indicating that the subject has been informed of the procedures to be followed, the experimental nature of the therapy, alternatives, potential benefits, side effects, risks, and discomforts.
2. Men or non-pregnant, non-breastfeeding women 18 to 75 years-of-age who are able to read and understand English.
3. Diagnosis of definite or probable bilateral essential tremor (ET) as defined by the Tremor Investigational Group with involvement of the hands and arms without present causes of enhanced physiologic tremor (Deuschl et al., 1998)
4. Diagnosis of ET before the age of 65
5. Tremor severity score of at least 2 in at least one upper extremity on at least one of the three maneuvers on the TETRAS scale
6. Total TETRAS performance score of at least 15. Note: Inclusion thresholds, including thresholds for items 5 & 6, should not be shared with study subjects or caregivers to limit Baseline inflation.

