4.5 Dose Adjustments / Toxicity Management

Adverse events will be graded for intensity by the investigator (see [Section 10.2.2.2](#)).

Dosing will be discontinued for all Grade 4 AEs.

In all subjects with intolerable AEs (as defined in [Section 10.2.1](#)) that are considered related to study drug, treatment should be suspended for up to 48 hours or until the AE resolves to a tolerable level of severity, whichever is earlier. Dosing may then be resumed at a previously tolerated lower dose (or 2 mg BID in the case of 4 mg BID). Only a single dose-step reduction (e.g. 10 mg BID to 8 mg BID, 8 mg BID to 4 mg BID, or 4 mg BID to 2 mg BID) is permitted. Re-up-titration is NOT permitted. Dosing should be discontinued if there is recurrence of intolerable AEs after dose reduction. Subjects on the 2 mg BID dose with intolerable AEs will be discontinued from treatment. Table 2 details dose reductions by dose level.

All subjects who discontinue treatment due to AEs will be followed for AE outcome. All AEs should be followed for resolution or for 30 days from the last dose of study drug, whichever is shorter.

Table 2: Study Drug Dose Reduction for Intolerable AEs

Dose and Schedule of Study Drug	Dose Reduction
2 mg BID	Remove from treatment ¹
4 mg BID	2 mg BID
8 mg BID	4 mg BID
10 mg BID	8 mg BID

1 – Subjects who are removed from treatment for AE(s) should be followed for resolution of the AE(s) and should complete all assessments scheduled for the EOS/FU Visit as well as all assessments that they are capable of completing on the Visit day if the decision to remove from treatment is made on a Visit day. Likewise, if the investigator plans to temporarily interrupt dosing because of an AE and the decision is made on a visit day, then the subject should complete all scheduled assessments that they are capable of completing on the visit day they appear.

The study safety representative should be notified of all dose reductions as soon as is feasible.

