(dosing days) orthostatic BP and pulse rate will be measured before dosing (recumbent and standing) and approximately 1-2 hours after dosing (recumbent and standing) as convenient between other required visit procedures. During any visit, blood pressure and pulse rate are to be assessed at any time subjects appear faint or complain of dizziness or other symptoms suggestive of hypotension. Respiratory rate and temperature will be measured in the recumbent position and need only be measured one time (with the first set of BP/pulse measurements). (Section 10.1.4.)

8. Clinical chemistry, hematology, urinalysis and coagulation panel. See Section 10.1.5 for complete details. Screening labs need not be repeated at Visit 1 (Day 1) if Day 1 is \leq 7 days from the screening visit. A positive drug screen will result in exclusion from the study unless it is explained by use of an allowed prescription medication (Section 10.1.6).
9. A triplicate 12-lead ECG will be performed at Screening and End of Study. At Visits 1, 2, 3 and 4 triplicate ECG will be performed predose and approximately 1-2 hours after the dose as convenient between other required visit procedures. All ECGs should be performed after at least 10 minutes of recumbency. (Section 10.1.8)
10. Women of childbearing potential only. A positive urine pregnancy test will be confirmed via serum testing. (Section 10.1.6)
11. Serum FSH only as needed to determine menopausal status in females < 62 years old with history of ≥ 12 months of amenorrhea without another cause.
12. Execution of the TETRAS Performance subscale will be video recorded for assessment by the central reader. Assessment by the site rater should be performed during the videotaping session. At Visit 1, the TETRAS Performance subscale should be performed prior to administration of study drug in the clinic. At Visits 3 and 4, the TETRAS Performance subscale should be performed during a window of 1 to 3 hours after administration of study drug in the clinic. (Section 8.1.1)
13. The Kinesia ONE device will be worn in the clinic after execution of the TETRAS Performance subscale assessment and, at Visit 1, prior to administration of study drug in the clinic. (Section 8.2.1)

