7.2.4 Visit 3 (Day 15 – End of Week 2)

Subjects will return to the clinic for assessments as detailed in Table 3. Subjects will have withheld their morning dose of study drug.

If the subject has been at least 75% compliant with the study drug regimen (as detailed in [Section 4.4](#)) and has not experienced any intolerable adverse events (as described in [Section 4.5](#)), the dose of study drug will be increased to 10 mg (or placebo) twice daily for the following two weeks. If compliance is determined to be less than 75%, up-titration should be discussed with the study safety representative.

Subjects will receive the first 10 mg dose of study drug (or placebo) and will then undergo efficacy assessments between 1 and 3 hours after dosing. Subjects will be followed for adverse events for at least 2 hours prior to discharge. Orthostatic VS and triplicate ECGs will be obtained 1 to 2 hours after dosing. The investigator or qualified designee will make the determination whether it is safe to release the subject from the clinic. Subjects will be instructed to take the second daily dose of study drug no closer than 10 hours and no later than 14 hours (every 12 hours \pm 2 hours) from the time of their first dose, and to continue taking 10 mg (or placebo) twice daily for the following two weeks (see Administration details in [Section 4.3](#)).

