7.2.5 Visit 4 (Day 28 – End of Week 4)

Subjects will return to the clinic for assessments as detailed in Table 3. Visit 4 is the end-of-dosing visit. Subjects will have withheld their morning dose of study drug. Subjects will receive the final dose of study drug (10 mg or placebo) and will then undergo efficacy assessments between 1 and 3 hours after dosing. Subjects will be followed for adverse events for at least 2 hours prior to discharge. Orthostatic VS and triplicate ECGs will be obtained 1 to 2 hours after dosing.

Visit must occur on or one day before Day 28 to ensure that all efficacy assessments occur while subject is still taking study drug.

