9 PHARMACOKINETIC AND PHARMACOGENOMIC ASSESSMENTS

9.1 Blood Sample Collection for Pharmacokinetic Assessments

All subjects will have one blood sample drawn prior to administration of CX-8998 at Visits 2, 3, and 4. Additionally, at Visit 4, a post-dose sample will be collected as close to 4 hours post-dose as possible, but within the window of 4-6 hours post-dose (i.e., a total of two PK samples are collected at Visit 4.)

For details on the timing, volume, handling, storage and methods of analysis of blood samples see the Laboratory Manual.

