9.2 Pharmacokinetic Parameters

Plasma concentrations of CX-8998 and its two primary metabolites (including, but not limited to, M01 and M02) will be determined.

The concentrations of CX-8998 and its metabolites in plasma will be summarized by visit and dose using descriptive statistics. The concentration data will also be used as part of an exploratory population pharmacokinetic/pharmacodynamic (PK/PD) analysis intended to evaluate the exposure-response and exposure-safety relationships; which will be reported separately from the Clinical Study Report.

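### Section 7.2.5 orders a 10 mg final dose at Visit 4 with no exception for subjects on a reduced dose, against the ban on re-up-titration in Section 4.5 and the synopsis

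*Protocol*

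**What the plan says.** The file holds several protocol versions. Everything below comes from the latest one, which plans about 106 subjects.

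- **Section 7.2.5 (Visit 4, Day 28).** Subjects withhold the morning dose and are dosed in the clinic: "Subjects will receive the final dose of study drug (10 mg or placebo) and will then undergo efficacy assessments between 1 and 3 hours", counted from that dose. The section has no tolerance condition, does not mention the subject's current dose, and does not refer to Section 4.3 or 4.5.
- **Section 4.5 and Table 2.** After a related intolerable adverse event, dosing may resume at a lower level: "Only a single dose-step reduction (e.g. 10 mg BID to 8 mg BID, 8 mg BID to 4 mg BID", with 4 mg going to 2 mg. The section then states: "Re-up-titration is NOT permitted. Dosing should be discontinued if there is recurrence of intolerable AEs after dose reduction".
- **Synopsis, Study Design.** It also rules out re-up-titration.
- **Section 7.2.4 (Visit 3, Day 15).** The step to 10 mg depends on at least 75% compliance and on the subject's tolerance so far ("and has not experienced any intolerable adverse events"), with a reference to Section 4.5. Section 7.2.3 treats the step to 8 mg in the same way.
- **Table 3, note 12.** For Visits 3 and 4 the note reads: "the TETRAS Performance subscale should be performed during a window of 1 to 3 hours after administration of study drug in the clinic".

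**The concern.** A subject whose dose was reduced and who is still on treatment at Visit 4 falls under two opposite instructions. The visit text names 10 mg. Section 4.5 says that the dose may not go up again.

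Two things are at stake. The first is safety. Section 10.2.1 defines an intolerable event as one related to study drug that is either Grade 3 or 4, or is Grade 1 or 2 and makes the subject want to stop. Grade 4 events end dosing under Section 4.5. The reduced subjects are therefore those with a Grade 3 event, or with a milder one that they no longer wished to bear, and the literal text would give them a higher dose. The second is the primary endpoint. The in-clinic dose comes 1 to 3 hours before the Day 28 TETRAS Performance rating, so such a subject would be rated after a dose that was not the one maintained.

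**Working it through.** No sample size, power or alpha figure enters this point, so there is no figure in the plan to reproduce. The check compares the texts and then takes simple dose ratios.

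**Step 1. Can a subject reach Visit 4 below 10 mg twice daily?** Yes. Section 4.5 and Table 2 allow one reduction, from 10 to 8, 8 to 4 or 4 to 2 mg twice daily, and treatment then continues. Only a recurrence of intolerable events after the reduction, or intolerable events at 2 mg, ends it.

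**Step 2. Does Section 7.2.5 exempt such a subject?** No. It contains neither a condition nor a cross-reference.

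**Step 3. Does another section supply the exemption?** Three places point to the intended reading:

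- Section 4.3 calls 10 mg twice daily a target and sends the reader to Section 4.5 for dose adjustments.
- Table 3, note 27 makes the step to 10 mg depend on tolerance.
- Table 3, note 26 says that at Visits 2, 3 and 4 the subject holds the morning dose because it will be given in the clinic. This suggests that the Visit 4 dose replaces the one withheld. The note gives no milligram figure, however, and at Visits 2 and 3 the clinic dose may be the new, higher level.

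None of the three says that it prevails over the 10 mg figure in Section 7.2.5.

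**Step 4. Size of the literal instruction.** Ratio = 10 mg divided by the dose in question. Capsules are 2 mg, so 10 mg is 5 capsules.

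| Reduction under 4.5 | Current dose at Visit 4 | Capsules, literal vs current | 10 mg / current dose | 10 mg / dose not tolerated |
|---|---|---|---|---|
| 10 to 8 mg | 8 mg | 5 vs 4 | 10/8 = 1.25 | 10/10 = 1 |
| 8 to 4 mg | 4 mg | 5 vs 2 | 10/4 = 2.5 | 10/8 = 1.25 |
| 4 to 2 mg | 2 mg | 5 vs 1 | 10/2 = 5 | 10/4 = 2.5 |

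In every row the literal dose is above the current dose, which Section 4.5 and the synopsis forbid. It also equals or exceeds the dose that prompted the reduction.

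**The case against.** The strongest reply is that the protocol already settles the dose. Section 4.5 is an explicit, capitalised prohibition, while the 10 mg in Section 7.2.5 is a parenthesis in a visit summary that describes the planned path. Sections 7.2.3 and 7.2.4 carry a condition because they order an increase; Section 7.2.5 orders only a final dose. With Section 4.3 and notes 26 and 27, a careful site would give the subject's own dose.

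Much of this stands. It shows what was intended and why the point is minor. It does not make Section 7.2.5 correct: staff running Visit 4 will work from that section, it states a figure, and they would have to override it from elsewhere in the protocol.

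A reader might be tempted to infer more. The documents do not support these readings:

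- **That re-escalation at Visit 4 is planned.** Every other dosing passage points the other way.
- **That the Visit 4 pharmacokinetic data are compromised.** Section 9.1 has a pre-dose sample and then "a post-dose sample will be collected as close to 4 hours post-dose as possible"; under Section 9.2 concentrations "in plasma will be summarized by visit and dose using descriptive statistics". Each sample can be classified by the dose that preceded it, so no error is shown.
- **That Section 7.2.4 needs a matching edit** for subjects never reduced but still on 4 mg at Visit 3. That group may be empty. Note 27 already requires 7 days at 8 mg before 10 mg, and the compliance rules in Sections 4.4 and 6.4 cover most routes into the group.
- **That a number of misdosed subjects can be given.** The protocol states no expected rate of dose reduction, and any count would also assume that sites disregard Section 4.5.

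**Conclusion.** The inconsistency is real, and Section 7.2.5 is wrong as written for any subject on a reduced dose. It is minor. At most it concerns one dose per affected subject, given in the clinic with at least 2 hours of adverse-event follow-up and with vital signs and ECGs 1 to 2 hours after dosing. A site that applies Section 4.5 will not give it.

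The dose ratios of 1.25, 2.5 and 5 hold only if a site follows the visit text literally. How many subjects would be concerned is not in the document. Neither the size nor the direction of any effect of one higher dose on the Day 28 score can be derived from it, so nothing follows about bias in the treatment comparison. The power calculation and the type I error rate are unaffected. This is a conflict between two passages and not a questionable design choice.

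**What to change.** In Section 7.2.5, replace the parenthesis that names 10 mg or placebo by: *(the subject's current dose of CX-8998 or placebo)*. No other section needs to change for this point.

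The cost is a few words. Schedule, sample size, blinding and analysis stay as they are. Reduced subjects are then dosed and rated at Visit 4 on their reduced dose, as Section 4.5 already implies.

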7.2.6 End of Study Visit (Day 35 – End of Week 5)

Subjects will return to the clinic for the final visit assessments detailed in Table 3. Adverse events that are unresolved at the end of study visit will continue to be followed by study staff as detailed in [Section 10.2.3](#).

7.3 Concomitant Medications and Other Restrictions

7.3.1 Concomitant Medications

Subjects may not be using more than one anti-tremor medication at the time of entry into the study. Subjects must have been on a stable dose for one month prior to screening and must have no change in dose in concurrent anti-tremor medication for the duration of the study. It should be noted that primidone is not a permitted anti-tremor medication.

Subjects may not use medications that might produce tremor or interfere with the evaluation of tremor, such as but not limited to: CNS-stimulants, lithium, amiodarone, metoclopramide, theophylline, and valproate.

On study visit days, subjects must refrain from use of medication/substance(s) that might produce tremor or interfere with the evaluation of tremor, such as but not limited to stimulant decongestants, beta-agonist bronchodilators, caffeine, alcohol and tobacco.

The stable use of a benzodiazepine, sleep medication or anxiolytic to improve sleep performance is allowed as long as tremor persists against the background of regular medication use. Subjects should not use sleep aids on the evening prior to a study visit.

The use of prescription or non-prescription drugs or other products (i.e. grapefruit juice) known to be strong inhibitors or inducers of CYP3A4 must be discontinued 2 weeks prior to Day 1 of dosing and withheld throughout the study. Subjects taking primidone for treatment of their ET may continue to do so at a stable dose. Subject randomization will be stratified by concomitant anti-tremor medication use and site type.

See [Appendix C](#) for a complete list of restricted inhibitors and inducers.

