7. One concomitant anti-tremor medication (other than primidone) is allowed. Note: Primidone is NOT an allowed anti-tremor medication. Subjects must have been on a stable dose for at least one month prior to screening and must have no change in dose in the single concurrent anti-tremor medication for the duration of the study. If on primidone, subjects are allowed to extend their screening period by 2 weeks (for a total of 6 weeks) and discontinue primidone under the supervision of the investigator.
8. Able and willing to comply with scheduled visits, treatment plan, laboratory tests, and other study procedures
9. Subjects with reproductive capability including all males and women of child-bearing potential (WOCBP) must agree to practice continuous abstinence or adequate contraception methods (appropriate double barrier method or oral, patch, implant, or injectable contraception) from as soon as feasible during screening period until at least 30 days after the last dose (i.e., intermittent abstinence based on “rhythm”, temperature monitoring, or other means of timing is not acceptable). WOCBP include any woman who has experienced menarche and who has not undergone successful surgical sterilization (hysterectomy, bilateral tubal ligation, and/or bilateral oophorectomy) or is not post-menopausal. Post-menopausal is defined as:
 - a. Amenorrhea \geq 12 consecutive months without another cause, and a documented serum follicle stimulating hormone (FSH) level > 35 mIU/mL;

b. Amenorrhea \geq 12 consecutive months in women \geq 62 years old (FSH testing is not required).

Male subjects with a partner of child-bearing potential must be surgically sterilized or be willing to use condoms with spermicide from as soon as feasible during screening period until at least 30 days after the last dose.

10. Approval by the sponsor medical personnel as to final suitability for the study

Exclusion Criteria

1. Exposure to tremorgenic drugs or drug withdrawal states within the 30 days prior to the first planned dose of study drug
2. Direct or indirect trauma to the nervous system within 3 months preceding the onset of tremor
3. History or clinical evidence of psychogenic tremor origin
4. Known history of other medical or neurological conditions that may cause or explain subject's tremor, including, but not limited to:
 - a. Parkinson's disease
 - b. dystonia
 - c. cerebellar disease, other than essential tremor
 - d. Traumatic Brain Injury
 - e. alcohol abuse or withdrawal

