6.2 Inclusion Criteria

Subjects may be included in the study only if they meet all of the following criteria. Subjects may undergo rescreening following consultation with and approval of the study safety representative.

- 1) Signed informed consent form (ICF) indicating that the subject has been informed of the procedures to be followed, the experimental nature of the therapy, alternatives, potential benefits, side effects, risks, and discomforts.
- 2) Men or non-pregnant, non-breastfeeding women 18 to 75 years-of-age who are able to read and understand English.

- 3) Diagnosis of definite or probable bilateral essential tremor (ET) as defined by the Tremor Investigational Group with involvement of the hands and arms without present causes of enhanced physiologic tremor ([Deuschl et al., 1998](#)).
- 4) Diagnosis of ET before the age of 65
- 5) Tremor severity score of at least 2 in at least one upper extremity on at least one of the three maneuvers on the TETRAS scale.
- 6) Total TETRAS performance score of at least 15 (Note: Inclusion thresholds, including thresholds for criteria 5 & 6 shall NOT be shared with study subjects or caregivers to limit Baseline inflation.)
- 7) One concomitant anti-tremor medication (other than primidone) is allowed. Subjects must have been on a stable dose for at least one month prior to screening and must have no change in dose in the single concurrent anti-tremor medication for the duration of the study. Note that primidone is NOT an allowed anti-tremor medication. If on primidone, subjects are allowed to extend their screening period by 2 weeks (for a total of 6 weeks) and discontinue primidone under the supervision of the investigator.
- 8) Able and willing to comply with scheduled visits, treatment plan, laboratory tests, and other study procedures

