6.3 Exclusion Criteria

Subjects will be excluded from the study if any of the following conditions apply. Subjects may undergo rescreening following consultation with and approval of the study safety representative.

- 1) Exposure to tremorgenic drugs or drug withdrawal states within the 30 days prior to the first planned dose of study drug

- 2) Direct or indirect trauma to the nervous system within 3 months preceding the onset of tremor
- 3) History or clinical evidence of psychogenic tremor origin
- 4) Known history of other medical conditions that may cause or explain subject's tremor, including, but not limited to:
 - a) Parkinson's disease
 - b) dystonia
 - c) cerebellar disease, other than essential tremor
 - d) Traumatic Brain Injury
 - e) alcohol abuse or withdrawal
 - f) mercury poisoning
 - g) hyperthyroidism
 - h) pheochromocytoma
 - i) head trauma or cerebrovascular disease within 3 months prior to the onset of essential tremor
 - j) multiple sclerosis
 - k) polyneuropathy
 - l) family history of Fragile X syndrome
- 5) Prior MR-guided Focused Ultrasound or surgical intervention (e.g., deep brain stimulation, ablative thalamotomy or gamma knife thalamotomy) for treatment of tremor
- 6) Botulinum toxin injection in the 6 months prior to screening
- 7) Currently using more than one anti-tremor medication
- 8) Experiencing clinical benefit from and/or is not willing to discontinue primidone
- 9) Use of medication(s) (in the past month) that might produce tremor or interfere with the evaluation of tremor, such as but not limited to: CNS-stimulants, lithium, amiodarone, metoclopramide, theophylline, and valproate
- 10) Inability to refrain from use of medication/substance(s) that might produce tremor or interfere with the evaluation of tremor on study visit days, such as but not limited to stimulant decongestants, beta-agonist bronchodilators, caffeine, alcohol and tobacco, based on investigator assessment at baseline
- 11) Positive urine drug screen (phencyclidine (PCP), cocaine, cannabinoids, opiates/barbiturates, benzodiazepines, amphetamines, methadone or MDMA (ecstasy)) unless explained by use of an allowed prescription medication ([Section 10.1.6](#)).
- 12) Regular use of more than two units of alcohol per day. See [Section 7.3.2](#) for definitions.

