- 13) Sporadic use of a benzodiazepine, sleep medication or anxiolytic to improve sleep performance. Stable use at a consistent dose is allowed as long as tremor persists against the background of regular medication use. Use on the evening prior to a study visit is prohibited.
- 14) Use of prescription or non-prescription drugs or other products (i.e. grapefruit juice) known to be strong inhibitors or inducers of CYP3A4 which cannot be discontinued 2 weeks prior to Day 1 of dosing and withheld throughout the study, including primidone
- 15) Concurrent illnesses that would be a contraindication to trial participation, including, but not limited to:
 - a) Severe arterial thromboembolic events (myocardial infarction, unstable angina pectoris, stroke) less than 6 months before screening
 - b) NYHA Class III or IV congestive heart failure, ventricular arrhythmias or uncontrolled blood pressure
 - c) Clinically significant ECG abnormality per the investigator assessment or any of the following:
 - i) QTcF >450 msec (males) or >470 msec (females)
 - ii) PR interval >250 msec
 - iii) Atrioventricular block of second degree or higher, including Mobitz I
 - iv) Persistent sinus bradycardia < 50 beats per minute; persistent means the bradycardia is present on the first ECG and on one repeat ECG performed on another day
 - v) For other ECG findings (e.g., including, but not necessarily limited to, tachycardia, bundle branch block, frequent ectopic beats, etc.) the investigator should send a scanned, identity-blinded copy of the ECG tracing to the study safety representative for review
 - vi) The presence of a cardiac pacemaker does not automatically exclude eligibility. The specifics must be discussed with the study safety representative to make a determination of eligibility.
 - d) Known infection with HIV, hepatitis B, or hepatitis C, unless curative therapy completed for hepatitis C with negative PCR
 - e) Significant hepatic (AST/ALT > 2X upper limit of normal) or renal disease (creatinine clearance <39 mL/min)
 - f) Significant psychiatric history including mood disorders and alcohol or substance abuse within the last year
 - g) A current C-SSRS score of 4 or 5 at screening, or history of suicide attempt at any time during the past year
 - h) Clinically significant impaired balance or is considered at increased risk for falls
 - i) Symptomatic orthostatic hypotension

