7.2 Summary of Treatment Visits

7.2.1 Screening

The Screening visit must be performed within 28 days of Visit 1/Baseline. Subject informed consent must be obtained prior to initiation of any study specified procedures. Subjects who are taking primidone at screening who are otherwise deemed eligible for participation and are willing to discontinue primidone will be allowed an additional 2 weeks of screening (a total of 6 weeks) to ensure safe primidone discontinuation. A central reviewer will confirm the TETRAS-related eligibility criteria prior to randomization. Screening results from all patients meeting the eligibility requirements will be further assessed by the sponsor medical personnel for final approval of suitability for inclusion in the study. Details of the eligibility review will be provided in the study Operations Manual. See [Table 3](#) for a detailed list of assessments to be performed.

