Appendix C – Cytochrome P450 Drug Interaction Table

PROHIBITED CYP3A4 INHIBITORS*

HIV antivirals (delavirdine, indinavir, nelfinavir, ritonavir)
amiodarone
cimetidine
clarithromycin
diltiazem
erythromycin
fluvoxamine
grapefruit juice
itraconazole
ketoconazole
nefazodone
suboxone
troleandomycin
verapamil

PROHIBITED CYP2C9 INHIBITORS*

amiodarone
fluconazole
izoniazid

PROHIBITED CYP3A4 INDUCERS*

carbamazepine
efavirenz
nevirapine
phenobarbital
phenytoin
pioglitazone
primidone
rifabutin
rifampin
St. John's Wort
troglitazone

PROHIBITED CYP2C9 INDUCERS*

rifampin
secobarbital

Prohibited moderate and strong inducers of CYP3A4 and CYP2C9 include the lists above but are not limited to the medications and agents listed

From: Flockhart DA. Drug Interactions: Cytochrome P450 Drug Interaction Table. Indiana University School of Medicine (2007). "/clinpharm/ddis/clinical-table/" Accessed [6 Dec 2016].

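### Section 7.3.1 lets primidone users continue at a stable dose, although the same section and the rest of the current protocol prohibit primidone

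*Protocol*

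**What the plan says.** The protocol file contains three successive versions. This point concerns only the last, which plans for approximately 106 subjects.

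Section 7.3.1 takes both positions. Its first paragraph says: "It should be noted that primidone is not a permitted anti-tremor medication". Its fifth paragraph first requires strong CYP3A4 inhibitors and inducers to be stopped two weeks before Day 1 and withheld for the whole study, and then continues: "Subjects taking primidone for treatment of their ET may continue to do so at a stable dose".

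The other current provisions point one way:

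- Section 6.2, inclusion 7: "Note that primidone is NOT an allowed anti-tremor medication". The synopsis repeats the rule.
- Section 6.3, exclusion 8, keeps out anyone "Experiencing clinical benefit from and/or is not willing to discontinue primidone". The synopsis repeats it.
- Section 6.3, exclusion 14, keeps out users of strong CYP3A4 inhibitors or inducers "which cannot be discontinued 2 weeks prior to Day 1 of dosing and withheld throughout the study, including primidone". The synopsis repeats it.
- Section 7.2.1: primidone users who are otherwise eligible and agree to stop "will be allowed an additional 2 weeks of screening (a total of 6 weeks) to ensure safe primidone discontinuation".
- Appendix C lists primidone by name among the prohibited CYP3A4 inducers and adds: "Prohibited moderate and strong inducers of CYP3A4 and CYP2C9 include the lists above".

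**The concern.** Section 7.3.1 is the text that sites work from. Note 24 to the Schedule of Assessments (Section 7.1) refers staff to Section 7.3 for prohibited and restricted medications and has them re-confirm other anti-tremor drugs at each visit. Staff who follow that pointer find a ban and a permission in the same section.

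A site that acted on the permission could dose a subject with study drug while the subject stayed on primidone. Two things make that undesirable. The protocol prohibits primidone as a CYP3A4 inducer, which implies a concern about CX-8998 exposure, although the text available does not quantify it. Section 1.1.3 also ranks primidone as Level A, the highest category there, for treating essential tremor, so it bears on the symptom that the primary endpoint measures.

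Such a subject could also be recorded as having concomitant anti-tremor medication, both in the randomisation stratum (Section 3.1) and in the ANCOVA covariate (Section 11.5.1.1). Neither separates primidone from permitted drugs. A site that followed exclusion 14 would have the same subject stop primidone or not enter, so two sites could treat identical patients in opposite ways, each with text to support it.

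**Working it through.** No arithmetic beyond a count applies. No alpha, power, SD or sample-size figure is involved.

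**1. Is the sentence live text?** Yes. It stands in Section 7.3.1 of the current version, so this is not a comparison with superseded wording.

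**2. Where does it come from?** It stands word for word in Section 7.3.1 of all three versions.

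| Version | Status of primidone | Stratification factor beside site type | Sentence in 7.3.1 |
|---|---|---|---|
| First (up to 92 subjects, target 8 mg BID) | allowed | primidone use | present, consistent |
| Second (up to 92 subjects, target 10 mg BID) | banned | any concomitant anti-tremor medication | present, contradictory |
| Current (approximately 106 subjects, target 10 mg BID) | banned | any concomitant anti-tremor medication | present, contradictory |

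The stratification sentence next to it was updated when primidone was banned. This sentence was not.

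**3. Can the statements be reconciled?**

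- *As a screening-only allowance:* no. Section 7.3.1 governs medication during the study, and an unchanged dose is the opposite of the supervised withdrawal for which screening is extended.
- *As an exception to the CYP3A4 rule it follows:* its position suggests this, but exclusion 14 names primidone within that rule, and Appendix C lists it as prohibited.
- *As covering subjects who have stopped:* no. It speaks of those still taking the drug. Equally, it does not license a restart.

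**4. Count of current statements.**

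| Barring primidone or requiring it to be stopped | Number |
|---|---|
| Synopsis, inclusion 7 | 1 |
| Synopsis, exclusions 8 and 14 | 2 |
| Section 6.2, inclusion 7 | 1 |
| Section 6.3, exclusion 8 | 1 |
| Section 6.3, exclusion 14 | 1 |
| Section 7.3.1, first paragraph | 1 |
| Appendix C | 1 |
| **Total** | **8** |

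Five further places lengthen screening to 6 weeks or 42 days so that primidone can be stopped: the synopsis study design, Section 3.1, Schedule note 3, Section 7.2.1 and Section 7.2.2. Statements permitting continued use: 1.

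Only exclusion 14, in the body and in the synopsis, names primidone together with the two-week timing and the requirement to withhold it throughout. The other provisions bar it or require it to be stopped without giving that timing.

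**The case against.** The best counter-argument is that hardly any subject could be affected. Someone still on primidone at Day 1 has already failed inclusion 7 and exclusion 14. Section 5.2 allows no one to be enrolled, randomised or dosed before central review confirms eligibility. Sponsor medical approval is itself an inclusion criterion, and Section 12.1.2 says that advance waivers are generally not granted. Anti-tremor drugs are re-confirmed at each visit, and Section 6.4 ends treatment when a prohibited drug is needed. A reader sent to Section 7.3 also meets the ban in the first paragraph and the reference to Appendix C at the end, so a query to the sponsor is more likely than continued primidone. The 8-to-1 count shows that the intended rule is clear.

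Most of this stands as a limit on frequency, but it does not make the sentence right. The safeguards would have to catch a site that is complying with Section 7.3.1 as written.

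Two narrower objections also have force. The protocol does not say how a non-permitted drug would be coded for stratification, and it leaves randomisation details to the Operations Manual. The stratum and covariate consequence is therefore a plausible inference, and the conclusion does not need it. The problem is also better described as an internal inconsistency than as a design fault, since the decision to exclude primidone is not in question.

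**Conclusion.** The contradiction is real and lies in operative text of the current protocol. One sentence permits what 8 other statements bar or require to be stopped, and no reading reconciles them. The intended rule is not in doubt, so correcting the sentence needs no design judgement.

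It should be corrected, but nothing here supports a stronger rating. Central review and sponsor approval should stop most such subjects at entry. The protocol gives neither the number of primidone users nor the size of the induction effect, so an effect on the primary comparison cannot be derived and none is claimed. The exposure concern is inferred from the prohibition itself.

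**What to change.** Delete the sentence from Section 7.3.1. Nothing need replace it, because exclusion 14 already sets the timing and treatment item 6 in Section 6.4 already covers a subject who needs a prohibited drug.

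If the sponsor prefers an explicit line, it could say that primidone must be stopped under investigator supervision at least 2 weeks before Day 1 and withheld throughout, with use on study handled under Section 6.4. Deletion is cleaner. A replacement would restate the two-week rule without addressing exclusion 1, which bars drug withdrawal states in the 30 days before the first dose.

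The cost is one sentence changed by amendment and a notice to sites. It needs no new data, visits, analyses or restrictions.
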